### **7.1.4. Subgroup Analyses**

The following subgroup analyses will be performed:

- Study site
- Gender
- Baseline BMI ( $< 35 \text{ kg/m}^2$  vs.  $\geq 35 \text{ kg/m}^2$ )
- Age ( $< 45$  years vs.  $\geq 45$  years)
- Race (white vs. all others)

Subgroup analyses of the first primary endpoint will be performed on the average of the five imputed datasets. For each subgroup, the subgroup and its interaction with treatment group will be added to the primary analysis model. A significant interaction with treatment group ( $p < 0.05$ ) will indicate that the mean %TBL differences between the Spatz3 and the control were not comparable between (among) the levels of the subgroup. If a significant interaction is found for any subgroup, additional analyses will be performed in an attempt to determine the cause of the interaction.

It should be noted that a formal subgroup analysis to compare subjects who did and did not receive a change in balloon volume must be assessed with caution. This is because the decision to have the change is optional and a meaningful comparison of its effect could only be done if subjects were randomized to volume addition or not. However, to characterize the risk profile of the Spatz3 and on its effect on weight loss, sub-group analyses by number of adjustments and on balloon volumes will be performed based on the following balloon volume sub-groups:

- 400-600 cc - includes mostly study subjects with initial filling volume only
- 601-800 cc – includes subjects who have had one additional adjustment
- 801-1000cc – includes subjects who have had at least 2 upward adjustments

These analyses will evaluate their effects on the first primary endpoint and on adverse events.

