The literature is filled with publications of the successful use of intragastric balloons outside of the US with wide ranging reports of 12-21 kg weight loss and 20-38 % EWL over 6 months, and with complication rates of up to 5 % [14 - 38]. Due to the wide range of published results, two comprehensive reviews of the BIB literature have been published in 2008 that meticulously scrutinized publications and chose studies based on multiple criteria such as controlled trials, randomization, low dropout rate, consecutive patients in series, etc [39,39]. Both review articles concluded that intragastric balloons are a “valuable” or “effective” non-surgical therapy for weight loss. Weight losses of approximately 8 to 16 kg, with 12% to 15 % weight loss and 20-30% EWL were noted in these “approved” studies. The reviewers reported 4.2% to 6.7% early balloon removals and an 8.1% deflation rate with 5 cases requiring surgery (4.1%). Studies have shown that a greater than 10% weight loss can prevent and reduce cardiovascular risks and other obesity-related diseases [41,41]. In the recently published FDA trials, the Reshape and Orbera reached their endpoints with  $\geq 25\%$  EWL in over 35% of treatment subjects with a superiority margin of  $> 7.5\%$  compared with control arm subjects (sham control in the Reshape trial and diet/exercise control in the Orbera trial). In the Reshape Duo balloon SSED published by the FDA the mean weight loss was 14.3 lbs/6 months with 25.1% EWL and 6.8% TBL compared with 11.3% EWL; 3.3% TBL and 7.2 lb weight loss in the control arm. Adverse events included nausea and vomiting in 85% of patients in the first 3 days post implantation. There were 7.5% serious adverse events requiring early device removal. 39.6% ulcerations were reported, however, following design change the ulceration rate fell to 10.3%. There was one episode of UGI hemorrhage from a gastric ulcer. The extraction procedure caused one contained esophageal perforation and one esophageal tear that was closed with endoscopic clips.

In the Orbera balloon SSED published by the FDA the mean weight loss was 16 lbs/6 months with 29 % EWL and 7.6 % TBL compared with 11.1% EWL; 3.1 % TBL and 6 lb weight loss in the control arm. Adverse events included nausea and vomiting in 85% of patients in the first 3 days post implantation. There were 5.6 % serious adverse events requiring early device removal including a gastric perforation leading to sepsis and surgery.

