### *4. 18- week adjustment*

At 18 weeks ± 4 weeks, all treatment arm subjects whose balloon has not been removed will be evaluated to determine if an upward adjustment is clinically appropriate. The following algorithm will be followed:

1. Subjects who have reached goal weight (calculated by BMI of 25) **and** are without any symptoms of gastroesophageal reflux or symptoms suggestive of gastritis or gastric ulcer, will not receive a balloon volume adjustment, and endoscopy at 18± 4 weeks will not be performed.
2. Subjects who underwent a prior unscheduled endoscopy with findings of a gastric ulcer will not receive an adjustment at 18± 4 weeks and no additional endoscopy beyond that described in section 2 above will be performed.
3. For all other subjects, endoscopy will be performed, and adjustments/treatment decisions will reflect the following algorithm:
  - a. For subjects with gastric ulceration found at endoscopy, **no upward adjustment** and PI will decide if balloon requires extraction based on endoscopic findings as described below.

Subjects who present with an endoscopically confirmed gastric ulcer will be treated as follows:

- **Ulcers whose smallest dimension (S) is  $\geq 2$ cm, or if there are any stigmata of increased risk of bleeding, such as visible vessels or clots**

The balloon should be extracted. Biopsy for H.pylori will be performed and treatment prescribed if positive.

These subjects should be treated with the following regimen: with sucralfate 1,000 mg PO Qid, and PPI medication twice daily for 3 months, followed by endoscopic evaluation after 3 months to confirm healing.

- **Ulcers whose smallest dimension (S) is  $\geq 1$  cm and  $< 2$  cm**

The balloon volume should be decreased by 150 ml (or 100 ml if starting volume is 400 ml) and subjects should be treated with the following regimen: sucralfate 1,000 mg PO Qid and increasing PPI medication to twice daily for 2 months. A biopsy for H.pylori will be taken and treatment prescribed if positive.

Endoscopic follow up will be performed at 8 weeks and if not healed at 8 weeks, an additional endoscopy at 16 weeks to confirm healing.

- At the 8-week follow-up, if signs of healing defined by a 25% reduction in either length or width are not observed, then the balloon should be extracted.

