#### *6. Follow-up Endoscopy*

All study subjects whose final adjusted volume is >900 ml will receive a follow-up endoscopic mucosal evaluation 4 weeks following the adjustment.

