#### **7.2. Sample size**

The true population mean %TBL in the control group is assumed to be 3.3% based on the Orbera and ReShape PMA studies. The standard deviation of %TBL is assumed to be approximately 6.6%, based on 6-month data from the Orbera PMA study. Based on these two assumptions, and a true population mean %TBL in the Spatz3 group of 10.34%, a total sample size of 240 subjects randomized 2:1 (160 in the Spatz3 group and 80 in the control group) will provide 80% power to demonstrate super-superiority of 4.5% TBL over the control at a one-sided significance of 2.5%. To account for a potential dropout rate of 15%, the final total sample size is 282 subjects randomized 2:1 (188 in the Spatz3 group and 94 in the control group).

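### The balloon-volume band analyses in 7.1.4 define neither the band nor the time at risk, so for complications that bar the 18-week increase or end in removal, higher volumes can look safer than they are

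*Combined protocol and SAP*

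**What the plan says.** Section 7.1.4 of the combined protocol and SAP plans that "sub-group analyses by number of adjustments and on balloon volumes will be performed based on the following balloon volume sub-groups": 400-600, 601-800 and 801-1000 cc. Each band carries a description by number of adjustments. The stated purpose is to describe the device's risk profile and its effect on weight loss: "These analyses will evaluate their effects on the first primary endpoint and on adverse events". The section warns that comparing subjects with and without a volume change needs caution, because the change is optional and not randomized. It says nothing about exposure time.

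Section 7.3 counts adverse events as each subject's first occurrence, by treatment group. The only time-to-event handling is the Kaplan-Meier ulcer rule in section 6.3.2, which pools all implanted subjects whatever their volume.

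How a subject comes to a given volume is set in section 4.3.3.2.5:

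- **Item 4 (18-week adjustment).** At 18 ± 4 weeks, "all treatment arm subjects whose balloon has not been removed will be evaluated to determine if an upward adjustment is clinically appropriate". Ulcer found earlier or at that endoscopy rules out the increase, as do erosive gastritis and esophagitis. Non-erosive gastritis and reflux controlled by medication do not. Symptom-free subjects at goal weight are not increased.
- **Items 1 and 2.** Intolerance that persists after medication and down-adjustment leads to extraction. Ulcers in the middle size range lead to a reduction of 150 ml, or 100 ml from a 400 ml start.
- **Item 3.** Subjects with no balloon effect on days 4-14 receive 250 ml early.
- **Item 6.** Subjects with a final volume above 900 ml "will receive a follow-up endoscopic mucosal evaluation 4 weeks following the adjustment".

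**The concern.** Volume here is partly a consequence of the outcome. A subject who has an ulcer in week 8 cannot be increased at week 18, and a subject extracted in week 8 is never assessed. Subjects who do reach a raised volume through the 18-week step have, by definition, come through the first months without such an event. If subjects are sorted by the volume they reached and events are counted per subject, the raised bands are credited with event-free time that was spent at the initial volume, and the lowest band collects the early failures.

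No other planned analysis relates balloon volume to risk. If the tabulation can reverse the direction of a real volume effect, readers could take reassurance about larger fills from a table that cannot give it.

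**Working it through.** The plan states no figure for the volume-band analyses, so there is none to reproduce.

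**Inputs**

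- Device arm: 188 (section 3.3), all taken as implanted.
- Times: increase at week 18, end at Week 32, so 14 weeks remain.
- Event risk by Week 32: 7.5%, range 5.6-10%. Section 2.2 reports, for one marketed balloon, "There were 7.5% serious adverse events requiring early device removal" and gives 5.6% for another. Both are six-month figures for other devices, used only for scale. The 10% upper value is an assumption.
- Share of remaining balloons increased: 85%, range 70-95%. This is an assumption; the documents give no figure.
- Constant weekly hazard; every event before week 18 prevents the increase.

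**Closed form, no effect of volume**

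1. h = -ln(1 - 0.075)/32 = 0.002436 per week.
2. Events before week 18: 188 × (1 - e^(-18h)) = 8.07, leaving 179.93.
3. Increased: 0.85 × 179.93 = 152.9. Not increased: 27.0.
4. Risk over weeks 18-32: 1 - e^(-14h) = 3.35%, which is 5.13 events among the increased and 0.90 among the rest.
5. Per-subject tabulation: not increased (8.07 + 0.90)/(8.07 + 26.99) = 25.6%; increased 3.35%. The ratio is 7.6, when the truth is 1.

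If the hazard doubles after the increase, the increased group's risk is 1 - e^(-28h) = 6.59%, and the unraised group still looks 25.6/6.59 = 3.9 times worse.

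| | No volume effect | Hazard doubled |
|---|---|---|
| 7.5%, 85% increased | 7.6 | 3.9 |
| Lowest ratio (10%, 70%) | 4.6 | 2.3 |
| Highest ratio (5.6%, 95%) | 16.6 | 8.4 |

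**Same events per balloon-week.** Time at initial volume is 188(1 - e^(-18h))/h + 26.99 × 0.0335/h ≈ 3,311 + 371 = 3,682 weeks. Time at raised volume is 152.94 × 0.0335/h ≈ 2,105 weeks. The rates are 8.97/3,682 and 5.13/2,105, both 0.24 per 100 weeks. With the hazard doubled, the raised rate is 10.09/2,070 = 0.49 against 0.24, so the true direction returns.

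**Check with the protocol's own volumes.** A simulation of 1,000,000 subjects applied the fill, increase and reduction rules. It assumed 10% ulcer risk by Week 32, 25% not increased for other reasons, half at least 64 inches tall, 20% with reflux, 5% given the early 250 ml, adjustment spread evenly over weeks 14-22, and 20% of ulcers extracted with the rest reduced.

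| | 400-600 | 601-800 | 801-1000 |
|---|---|---|---|
| No effect: risk by maximum volume | 19.5% | 5.3% | 4.5% |
| No effect: events per 100 weeks at current volume | 0.33 | 0.33 | 0.33 |
| Hazard doubled: risk by maximum volume | 20.5% | 9.4% | 8.9% |
| Hazard doubled: events per 100 weeks at current volume | 0.35 | 0.60 | 0.67 |

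**The banding rule matters.** A reduction takes 400, 450 and 500 ml to 300, 300 and 350 ml, below every band. If final volume sets the band, 5.8 of 18.7 expected ulcers (31%) fall in no band in the no-effect simulation. An ulcer arising at 850 ml (550 + 300) would be filed at 700 ml, and one arising at 700 ml (450 + 250) at 550 ml, in the lowest band. The band descriptions do not settle the rule: one 18-week increase reaches 850 ml, yet the top band is described as two or more increases, and 400 + 200 = 600 ml stays in the lowest band after an increase.

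**Where the pattern is absent.** For an event that does not bar the increase (50% risk, no volume effect), the simulated risk by maximum volume is 50% in all three bands.

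**The case against.** The strongest reply is that the plan never says it will tabulate simple proportions by maximum volume. That is correct: 25.6% against 3.35% is what one natural reading produces, not a figure the plan commits to. The supportable defect is that the band rule and the denominator are undefined, and that the per-subject readings mislead for this class of event.

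A reader might infer that all complications collect in the lowest band by construction. The documents do not support that. Accommodative symptoms, controlled reflux and non-erosive gastritis do not bar the increase. The early 250 ml takes some subjects to 650-800 ml within weeks. Reduced balloons can fall outside every band. Two mechanisms push the other way: events that happened before the increase can be charged to the higher band, and the extra endoscopy above 900 ml finds more silent ulcers there.

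A reader might also infer that the upper bands are credited with weight loss. Goal-weight subjects stay low, subjects without balloon effect move up early, and early explants are treated as dropouts with Week 32 imputed (section 7.1.2). These act in different directions, and the net direction has not been shown.

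The section's caution deserves credit, and these tables are descriptive. But the caution concerns non-random choice of volume. Misallocated time at risk is a separate error that can be corrected without randomization.

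**Conclusion.** The point holds in a limited form. For gastric ulcer, erosive gastritis, esophagitis and unresolved intolerance, the protocol's rules keep early cases out of the bands reached through the 18-week increase, and section 7.1.4 has nothing that corrects for it. A per-subject tabulation can then favour higher volumes even where they are more harmful. The ratios (4.6 to 16.6 with no effect, 2.3 to 8.4 with a doubled hazard) rest on a constant hazard, event rates from other devices or assumed, and an assumed share increased. The direction is the finding; the size is illustrative.

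No conclusion is drawn on events that do not bar the increase or on the direction of %TBL bias. Neither co-primary test uses these bands, so both are unaffected.

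**What to change.** Amend section 7.1.4 as follows:

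- Define balloon volume as time-varying. Attribute each adverse event to the volume in place at onset, before any reduction made in response to it.
- Report events per balloon-week at that volume, separately for before and after the 18-week adjustment.
- Add an analysis category below 400 ml, and reconcile the band descriptions with the volumes that one or two increases actually produce.
- For %TBL, use a landmark at the 18-week evaluation, restricted to subjects with the balloon in place and still eligible for an increase. The outcome is change from that visit to Week 32. State that the comparison remains non-randomized, since confounding by indication is reduced but not removed.
- List ulcers found only at the follow-up endoscopy above 900 ml separately.

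The cost is analysis wording and a little more programming. Implant, adjustment, extraction and event dates, with the volumes, arise from the procedures themselves, so no visit is added. The drawback is sparse events in some volume-by-period cells.

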**Note: The Maximum final volume of the balloon must not exceed 1,000 ml.**

Subjects who received an additional 250 ml in the first month for lack of any balloon effect will undergo an 18-week adjustment; however, their maximum final volume cannot exceed 1,000 ml. For example, a subject who started with 550 ml and then received 250 ml addition after 2 weeks due to lack of effect, cannot receive more than 200 ml addition at 18 weeks even if they do not have GE reflux symptoms and are  $\geq$  64 inches.

5. *Adjustment procedure*

The balloon adjustment procedure is done with an endoscopy procedure under the same sedation as the implantation procedure.

The adjustment procedure requires the patient to be on the following dietary restrictions:

- 72 hours prior to the procedure: Soft food only, no meat or vegetables in any form.
- 48 hours prior to the procedure: Full liquids only.
- 24 hours prior to the procedure: Clear liquids only.
- 12 hours prior to the procedure: No food or liquids by mouth.

The adjustment procedure is performed under conscious sedation by the anesthetist similar to the implantation procedure. The endoscope is introduced in the usual manner. The capped valve is identified and the suture loop is grasped with a standard rat tooth grasping forceps. The scope and cap are pulled out of the mouth, (the inflation tube stretches and reaches the mouth – see section 5.1) wherein the cap is twisted off and replaced with the extension tube (provided). The extension tube is lowered down the throat into the esophagus followed by the scope. The adjustment commences by utilizing the 3-way stopcock on the proximal end of the extension tube. Following completion of the adjustment, the extension tube is pulled out of the mouth and is replaced by the cap. The cap is lowered back into the throat and allowed to pull itself back to its position touching the white catheter. The scope then pushes it down into the stomach.

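### The comparison of endoscopically found lesions by number of balloon adjustments and volume band (7.1.4) is distorted by unequal endoscopy counts and by lesions determining the volume, in a direction that cannot be predicted

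*Combined protocol and SAP*

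**What the plan says.** Section 7.1.4 announces that "sub-group analyses by number of adjustments and on balloon volumes will be performed based on the following balloon volume sub-groups": 400-600, 601-800 and 801-1000 cc. It adds that "These analyses will evaluate their effects on the first primary endpoint and on adverse events". The stated purpose is to describe the device's risk profile and its effect on weight. Section 7.1.4 warns that a comparison of subjects with and without a volume change "must be assessed with caution", because the change is optional and not randomized. It does not mention how often each group is examined, nor that a lesion can decide the group.

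The rules that matter are in section 4.3.3.2.5:

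- Item 5: "The balloon adjustment procedure is done with an endoscopy procedure under the same sedation as the implantation procedure".
- Item 6: "All study subjects whose final adjusted volume is >900 ml will receive a follow-up endoscopic mucosal evaluation 4 weeks following the adjustment".
- Item 4, subjects at goal weight without symptoms: they "will not receive a balloon volume adjustment, and endoscopy at 18± 4 weeks will not be performed".
- Item 4, earlier ulcer: "Subjects who underwent a prior unscheduled endoscopy with findings of a gastric ulcer will not receive an adjustment".
- Item 4, the rest: "For all other subjects, endoscopy will be performed, and adjustments/treatment decisions will reflect the following algorithm".

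Under item 4, volume is added only where there is no gastric ulcer, erosive gastritis or esophagitis of any grade. Items 2 and 4 prescribe a volume decrease and repeat endoscopies for the two intermediate ulcer classes. Section 4.3.3.2.6 includes a mucosal inspection at extraction for everyone. Stomach and esophageal ulcers are listed adverse events (6.2.2, Table 1), and section 7.3 counts the first occurrence per subject.

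**The concern.** An asymptomatic mucosal lesion is recorded only if someone looks. Where the grouping variable partly sets the number of looks, groups can differ in recorded lesions with no difference in true risk. Because adverse events are counted as first occurrence, an extra look can only raise a subject's chance of being counted.

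A second problem runs alongside. A lesion found at 18 weeks keeps the subject out of the group receiving an addition, and some ulcers move the subject to a lower volume. If subjects are then grouped by final volume or final number of adjustments, the outcome has helped to define the exposure.

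At stake is the safety description of the feature that distinguishes this device, its adjustability. The primary endpoints are not affected, and neither is the ulcer stopping rule in 6.3.2, which pools all implanted subjects.

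**Working it through.** The plan gives no lesion rates for these groups, so there is no figure of its own to reproduce on this point. The look counts below come from the protocol. Every lesion rate is an assumption.

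**1. Planned looks after implant** (balloon kept to week 32, no unscheduled endoscopy)

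| Path | Endoscopies | Looks |
|---|---|---|
| At goal weight, symptom-free, no early addition | extraction | 1 |
| No addition | 18 weeks, extraction | 2 |
| One 18-week addition | 18 weeks, extraction | 2 |
| Early 250 ml addition only | early, 18 weeks, extraction | 3 |
| Early and 18-week additions, final volume up to 900 ml | early, 18 weeks, extraction | 3 |
| Early and 18-week additions, final volume above 900 ml | early, 18 weeks, 4 weeks later, extraction | 4 |

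The 18-week endoscopy precedes the decision to add volume, so the commonest contrast (none against one 18-week addition) has equal looks.

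**2. Who gets the fourth look.** A single addition reaches at most 550 + 300 = 850 ml. Exceeding 900 ml takes two: 450 + 250 + 250 = 950, 500 + 250 + 200 = 950, or 550 + 250 + 200 = 1,000. The 801-1000 cc band therefore mixes subjects with 2 looks (850 ml by one addition), 3 looks (450 + 250 + 200 = 900) and 4 looks.

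**3. Who has only one look.** Reaching BMI 25 from an entry BMI of 30 needs a loss of 1 − 25/30 = 16.7%; from just under 40 it approaches 1 − 25/40 = 37.5%. Section 7.2 assumes a mean loss of 10.34% with SD 6.6%, and that is at week 32. Even the smallest required loss is (16.7 − 10.34)/6.6 = 0.96 SD above that mean, and it must occur by 18 ± 4 weeks. The group is probably small.

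**4. Effect of looks alone, volume having no effect**

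- Independent, equally informative looks with detection probability p: the 4-to-2 ratio is [1 − (1 − p)^4]/[1 − (1 − p)^2] = 1 + (1 − p)^2, which cannot exceed 2. At p = 3% it is 11.5%/5.9% = 1.94; at p = 5%, 18.5%/9.8% = 1.90.
- Lesions arising evenly over 32 weeks and visible for 8 weeks, looks at weeks 2, 18, 22 and 32: two looks (18, 32) cover 8 + 8 = 16 of 32 weeks; four cover 2 + 12 + 8 = 22. The ratio is 22/16 = 1.4. With 4-week visibility it is 14/8 = 1.75; with 12 weeks, 28/24 = 1.17. Simulation over incidence 5-20% and visibility 4-12 weeks gave about 1.2 to 1.8.

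**5. Effect of the lesion rule.** Assume 10% incidence over 32 weeks, 8-week visibility, 5% at goal weight, and 10% given no addition because of uncontrolled reflux. A lesion is then visible at week 18 in 10% × 8/32 = 2.5%. Take 1,000 subjects without an early addition:

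- 50 are at goal weight and are examined only at extraction: 50 × 2.5% = 1.25 lesions.
- 950 are examined at 18 weeks; 23.75 have a lesion and receive no addition.
- Of the other 926.25, 92.6 are held back for reflux. Their lesion rate at extraction is 2.5/97.5 = 2.56%, giving 2.4 lesions.
- The remaining 833.6 receive an addition, with the same 2.56% at extraction.

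No upward adjustment: (1.25 + 23.75 + 2.4)/(50 + 23.75 + 92.6) = 27.4/166.4, about 16.5%, against about 2.6% after one 18-week addition. A simulation that adds 15% early adjusters, and treats every double adjuster as above 900 ml, gives 16.4%, 3.1% and 3.8% for 0, 1 and 2 upward adjustments. Over the assumed ranges these are 4.7-39.5%, 0.8-9.2% and 1.3-8.9%.

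**6. Counting downward adjustments too.** The same simulation then gives 2.5%, 5.2% and 6.5% for 0, 1 and 2 adjustments. The pattern reverses on a definition that 7.1.4 leaves open, and the rise comes largely from the ulcer that caused the adjustment.

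**The case against.** The strongest reply is that 7.1.4 already calls for caution, sets no test threshold or success criterion for adverse events by volume, and offers the analysis as description. That stands, and it limits the importance of the point. But the caution concerns optional, non-randomized volume change. It would not alert a reader to unequal examination or to lesions that set the volume.

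A second reply is that most subjects have the same two looks. This is correct for none against one 18-week addition, and it confines the ascertainment problem to early adjusters and to volumes above 900 ml.

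A reader might infer something stronger: that recorded lesions must rise with adjustments and volume by construction, up to 3.7- to 3.8-fold (4 looks against 1, at 3-5% per look). The documents do not support this. Unadjusted subjects normally have the 18-week endoscopy too, the one-look group is probably small, and the lesion rule pushes findings toward lower volumes. Nor is the early look, after about two weeks of exposure, as informative as a later one.

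It might also be argued that opposing distortions cancel. Nothing in the documents shows that they do, and their relative size is unknown.

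**Conclusion.** The point holds in limited form. The comparison of endoscopically detected lesions by adjustment count and volume band mixes any volume effect with two protocol artefacts: unequal looks, and volume determined by the lesion itself. Looks alone account for at most about a 2-fold difference for 4 against 2 looks, and about 1.2- to 1.8-fold in the less idealized calculation. The lesion rule can act more strongly and in the opposite direction across upward-adjustment groups, so higher volumes could appear falsely safe as easily as falsely harmful.

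The look counts are protocol facts. The incidence, visibility and subgroup fractions are assumptions, and unscheduled endoscopies were not modelled. This warrants an analysis change, since the volume comparison will otherwise be read as a safety statement on adjustability.

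**What to change.** In 7.1.4, for gastric ulcer, erosive gastritis and esophagitis:

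1. Classify each first lesion by the balloon volume and number of adjustments in place immediately before the endoscopy that found it, not by later or final values.
2. State whether downward adjustments count.
3. Tabulate the number of endoscopies per volume and adjustment group.
4. Report lesions found only at the early-addition endoscopy or the 4-week endoscopy above 900 ml separately from those found at 18-week, extraction and symptom-driven endoscopies.
5. Do not use lesions per endoscopy with ulcer-healing follow-up endoscopies in the denominator; those repeat looks follow from the lesion. Do not group 18-week findings by the volume reached afterwards.
6. Extend the existing caution to ascertainment and reverse causation.
7. Keep full incidence as a listing.

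The band descriptions also need reconciling with the algorithm. A volume of 850 ml is reachable by one addition but falls in the band described as needing at least two. Reduced volumes of 300-350 ml fall in no band. Section 5.1.1 gives a 900 ml maximum where 4.3.3.2.5 gives 1,000 ml.

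The cost is SAP wording and one extra table from data already collected, with smaller counts in the compared groups. The comparison remains non-randomized.
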